1) Protocol Title

Effects of liposomal bupivacaine for acute pain in hip and femur fractures: a randomized, active comparator-controlled, blinded trial

DoD Additional Requirement:

This is an investigator initiated, single-center study funded by the United States Department of Defense Health Program. The UC Davis PI and research staff are aware of specific DoD requirements and confirm that all additional criteria for DoD research have been met.

2) Author of Protocol

- UC Davis Researcher**
- Researcher from other institution**
- Private Sponsor**
- Cooperative Group**
- Other: Volunteer Associate Clinical Professor**

3) IRB Review History

This is our first revision to the initial submission to the IRB.

4) Objectives

This is an investigator-initiated, single-center, randomized, patient blinded, controlled trial. The purpose of this study is to compare the effect of a fascia iliaca compartment block (FICB) using 0.2% ropivacaine vs. liposomal bupivacaine in patients with femur and/or hip fractures admitted to the University of California Davis Medical Center (UCDMC). The primary endpoint will be the total opioid requirements during the 96 hour randomization period with secondary endpoints including total daily opioid requirements for days 1-4, duration of effect and objective pain scores using the numeric rating scale (NRS) during their hospital stay.

Hypothesis: In patients with femur or hip fractures, a fascia iliaca compartment block using liposomal bupivacaine will result in less total opioid administration during the randomization period compared to a fascia iliaca compartment block using 0.2% ropivacaine.

The long-term goal of this study is to provide pilot information to guide and design larger, multicenter trials which will evaluate the utility and cost-effectiveness of long acting liposomal bupivacaine as an opioid-sparring analgesic strategy in injured trauma patients. Ultimately, it is hoped that this information can improve safe and effective narcotic sparing analgesia in the awake, combat casualty, as well as serve as primary steps towards

evaluating broader considerations for liposomal analgesia to improve short- and long-term outcomes in these patients.

5) Background

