Duration anticipated to enroll all study subjects: 12 months.

Data acquisition and analysis: same 12 months

Manuscript preparation: 6 months

Total time requirement: 1.5 years

11) Study Endpoints

Hypothesis: In patients with femur or hip fractures, a fascia iliaca compartment block using liposomal bupivacaine will require less total opioid administration compared to a fascia iliaca block using 0.2% ropivacaine.

Primary Endpoint

(1) Total opioid requirement during the 96 hour randomization period measured in milligram morphine equivalents.

Secondary Endpoint

(1) Percentage of time during the 96 hour randomization period that the objective pain score was above mild (defined as a numeric rating score >4).

12) Procedures Involved

The nature of the risks and benefits associated with participation in the study will be explained to all potential study subjects. Written informed consent must be obtained before the subject can begin any screening procedures that are not considered standard patient care. Subjects who have undergone the screening procedures and have met the entry criteria will be randomized into the study and assigned to treatment by the Unblinded Pharmacist. Subjects will be randomized in a computer-generated, blinded block, 1:1 ratio to treatment with 60mL of either 0.2% ropivacaine (120mg) or a dilution of liposomal bupivacaine (266mg).

The Pharmacy and Emergency Medicine (EM) members will be the only unblinded study team members. All other members, including the Trauma team and Clinical Research Coordinator (CRC), will remain blinded.

The unblinded Investigational Drug Service (IDS) Pharmacy at UC Davis Health (UCDH) will be responsible for blinding and drug preparation. Investigational Product (IP) will be prepared in three 35mL Luer lok syringes, each containing 20mL of IP, for a total dose of 60mL. In addition to a patient-specific institutional label, masking/amber tape will also be affixed to the syringes in order to reduce the risk of drug recognition by a supporting procedure nurse. During the procedure, nursing care of the patient will temporarily transition from the primary bedside nurse to a supporting procedure nurse. The supporting procedure nurse will remain blinded and will assist primarily with assessments and recording of vital signs (but will not work directly with the IP).

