Additional outcomes: hospital lengths of stay; time from study drug initiation to maximum allowable ambulation per injury pattern; post-discharge opioid type and dosage provided at the time hospital discharge prescription; and patient report of chronic pain syndromes. Adverse effects including the incidence of hypertension requiring antihypertensive pharmacotherapy in addition to the patients home regimen, hypotension (SBP < 90 mmHg) requiring fluid bolus/vasoactive pharmacotherapy, tachycardia requiring pharmacologic intervention (defined as HR greater than 100 bpm), bradycardia (defined as HR below 60 beats per minute with symptoms or hypotension), respiratory depression (apnea; transition to higher level of respiratory support), emesis, hallucinatory reactions or experiences per patient interview, and pruritus per physical exam.

The study will be stopped if ≥2 patients receiving the active study drug develop the same Grade 3 adverse reaction (Adverse Event Severity

Definition defined previously) or if one patient develops a Grade 4 or higher adverse reaction.

13) Data and Specimen Banking

Not applicable.

14) Data Management and Confidentiality

Each patient will be assigned a unique study ID number at the time of study entry. Study information stored by the research personnel at UCDMC, which may include name and medical record number, will be kept strictly confidential and available only to the principal investigator and trained staff assigned to this study. All information will be kept secure in locked file cabinets accessible only by research personnel. All identifiers for recruitment purposes will be destroyed within 2 years of completion of study.

Statistical Analysis

Data will be presented as means \pm standard errors of the mean (primary endpoint) and proportions \pm interquartile ranges (secondary endpoint). Following assessment for normality, primary endpoint data will either be subjected to parametric unpaired two-sided t-tests or nonparametric Wilcoxon rank sum test Mann-Whitney two sample statistic. Significance will be set at $p = 0.05$. Secondary endpoint proportions will be assessed using either nonparametric chi-square tests or Fisher's exact test.

Other data such as ICU and hospital lengths of stay and adverse events will be collected, summarized, and described. Exploratory analyses these data may be attempted, but these will be hypothesis generating, given the small sample size used in this pilot study.

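### Sections 4 and 11 name different secondary endpoints, and the only secondary test planned (chi-square or Fisher's exact) suits none of them as described

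*Combined protocol and SAP*

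**What the plan says.** Section 4 (Objectives) names "secondary endpoints including total daily opioid requirements for days 1-4, duration of effect and objective pain scores using the numeric rating scale (NRS"), and sets the pain scores over the hospital stay. The word introducing the list leaves it open-ended.

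Section 11 (Study Endpoints) has one numbered secondary endpoint: "Percentage of time during the 96 hour randomization period that the objective pain score was above mild", with above mild defined as NRS greater than 4. Daily opioid totals and duration of effect do not appear there.

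The primary endpoint is the same in both sections: "Total opioid requirement during the 96 hour randomization period measured in milligram morphine equivalents".

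The Statistical Analysis text under Section 14 splits the tests by endpoint type. For the primary, "primary endpoint data will either be subjected to parametric unpaired two-sided t-tests or nonparametric Wilcoxon rank sum test". For the secondary, "Secondary endpoint proportions will be assessed using either nonparametric chi-square tests or Fisher's exact test", with proportions and "interquartile ranges (secondary endpoint") as the summary. It adds "Significance will be set at $p = 0.05" and gives no testing order or multiplicity rule. Its caveat about hypothesis-generating analyses is attached to other data, such as lengths of stay and adverse events.

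**The concern.** There are two separate faults.

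First, a reader of the final report could not tell from the plan which secondary result was pre-specified. The daily totals matter here. Section 5 gives 4 to 8 hours for standard local anesthetics and up to 96 hours for the liposomal product, so on the plan's own rationale any separation should show mainly after the first hours. Four daily comparisons invite attention to whichever day looks best. Section 4 says the trial is meant to inform the design of larger multicenter trials, so a secondary signal chosen after the data are seen could misdirect that design.

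Second, the test does not match the endpoints. Chi-square and Fisher's exact tests compare counts of independent units in categories. A daily milligram total and a duration are not counts. A percentage of time is one number between 0 and 100 for each patient, so it is not a count of patients either. It becomes one only if patients are classed as responders (no cut-off is given) or if repeated NRS readings are pooled as though each were a separate patient.

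**Working it through.** The plan gives no error-rate figure for the secondary endpoints, so there is none to reproduce. The check is a comparison of the text followed by two illustrations of size.

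**Text side by side**

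| Item | Section 4 | Section 11 | Test named for it |
|---|---|---|---|
| Daily opioid totals, days 1 to 4 | yes | no | none |
| Duration of effect | yes, not defined in the text supplied | no | none |
| NRS scores over the stay | yes | no | none |
| Percent of 96 h with NRS above 4 | no | yes | chi-square or Fisher's exact |

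No row is present in both sections. The last two rows share the topic of pain but differ in form (scores against percentage of time) and window (hospital stay against 96 hours).

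**Size of the choice**

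Candidate comparisons: 4 daily totals + 1 duration + 1 NRS over the stay + 1 percent-of-time = 7. The level is 0.05 each (Statistical Analysis). For k independent tests, the chance of at least one false positive is 1 − 0.95^k:

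- k = 4 (daily totals alone): 1 − 0.95^4 = 18.5%
- k = 6 (Section 4 list): 1 − 0.95^6 = 26.5%
- k = 7 (both lists): 1 − 0.95^7 = 30.2%

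These endpoints come from the same patients and should be positively correlated, which lowers the figures. The documents give no correlations, so a range was assumed. A simulation with t-tests, 17 patients per arm (Section 7), equal pairwise correlation and 20,000 runs gave:

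| Assumed correlation | 6 tests | 7 tests |
|---|---|---|
| 0.3 | 24.4% | 27.5% |
| 0.5 | 21.0% | 23.8% |
| 0.7 | 16.9% | 18.5% |
| 0.9 | 11.0% | 11.6% |

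With one pre-specified secondary endpoint and a suitable test, the figure is 5%.

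**Size of the test mismatch if readings are pooled**

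Section 12 has pain scored every four hours while awake, so at most 96 / 4 = 24 readings per patient. If patients are awake for two thirds of the time (an assumption), it is 16. Pooling 24 readings treats 17 × 24 = 408 readings per arm as independent when there are 17 patients. With m readings per patient and within-patient correlation ICC, the variance is understated by the factor 1 + (m − 1) × ICC:

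- m = 16, ICC = 0.1: 1 + 15 × 0.1 = 2.5
- m = 24, ICC = 0.5: 1 + 23 × 0.5 = 12.5

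A simulation of 4,000 runs, with an assumed true proportion of 0.4 in both arms, gave a type I error of 21.8% in the first case and 58.6% in the second. With ICC = 0 it stayed near 5% (4.9% for m = 16, 4.4% for m = 24), so the inflation comes from the clustering.

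**The case against.** The strongest reply is that the documents do lean one way. Section 11 is the formal endpoint section and names one endpoint, and the Statistical Analysis text refers to a single secondary endpoint summarised as a proportion. On that reading Section 4 is loose narrative, and percent-of-time is simply its pain item made operational. This is a fair reading and supports keeping the Section 11 endpoint. It does not remove the conflict: Section 4 expressly calls its items secondary endpoints, no sentence gives Section 11 precedence, and the exploratory caveat does not name the Section 4 items.

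A reader might infer that the daily totals have no valid test at all. The documents do not support that. The t-test or Wilcoxon test named for the primary would suit a daily milligram total; the plan just does not assign either test to it. The gap is in pre-specification.

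A reader might also infer that four or seven tests will be run and the best one reported. No section says so. The percentages above show what the ambiguity permits, and the count of seven includes two versions of the same pain data.

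Finally, this is a 34-patient pilot whose primary endpoint is stated consistently. That lowers the stakes but does not settle which secondary result counts.

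**Conclusion.** The point stands as an inconsistency in the secondary endpoints plus a test that does not fit them. The two lists differ without being wholly separate, since both include NRS pain. The mismatch extends to the Section 11 endpoint itself, so choosing that list alone would not cure it. The plan's own summary by interquartile range treats percent-of-time as a spread of patient values, which the planned test does not.

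On size, testing every candidate at 0.05 would give about a 30% chance of at least one false positive if the seven were independent, and about 12% to 27% for assumed correlations of 0.9 to 0.3. Pooled readings would give a type I error of roughly 22% to 59% under the assumed reading counts, proportion and ICC range of 0.1 to 0.5. None of the correlations, the ICCs or the 0.4 proportion comes from the documents, and the plan does not say that readings would be pooled.

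The error rate of the primary comparison is not affected by this point. The plan should be corrected, but the fault does not undermine the main result.

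**What to change.** - Use one secondary list in Section 4, Section 11 and the Statistical Analysis text. Keep percent of the 96 hours with NRS above 4 as the single secondary endpoint.
- Replace chi-square/Fisher for that endpoint with a Wilcoxon rank-sum test (or t-test) on one percentage per patient. State how readings taken while awake are turned into time, and what denominator applies if a patient leaves before 96 hours, since Section 10 ends participation at discharge.
- Label daily opioid totals, duration of effect and NRS over the stay as exploratory, and define duration of effect.
- Report the daily totals from one repeated-measures analysis, with an estimate and 95% CI for each day, in place of four separate tests. It must handle days with no opioid use and days after discharge, for example by an untransformed or rank-based analysis. A plain log transform would fail on zero-opioid days.

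If the sponsor prefers to keep several items as secondary, a Bonferroni level would be 0.05 / 6 = 0.0083 for the Section 4 list or 0.05 / 7 = 0.0071 with percent-of-time added. Either would be demanding with 17 patients per arm.

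The cost is wording in three places and one extra analysis. Section 12 already provides for collecting the opioid amounts and NRS scores.

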The duration of standard local anesthetic formulations vary from 4-8 hours and administration can include single injections or continuous infusion catheters. Liposomal bupivacaine, Exparel®, has a prolonged duration of action of up to 96 hours. Studies have verified its safety with a very low risk of dysrhythmias, local tissue reaction, effects on wound healing or nerve toxicity. In the elective surgical setting, liposomal bupivacaine has been shown to have an opioid sparing effect, increased duration of analgesia, increased patient satisfaction, earlier discharge, and lower hospital cost. This formulation has not been studied in trauma patients and its novel use may impact practice in pain management of trauma patients. Patients may exhibit a lower opioid requirement with the use of the liposomal bupivacaine. In addition, this may reduce the incidence of untoward effects including respiratory depression, central nervous system depression, and gastrointestinal dysfunction, and subsequently speed recovery with improved mobilization and cooperation with physical therapy. To date, no studies have evaluated liposomal bupivacaine regional analgesia following extremity trauma. This pilot study aims to assess the

efficacy of long-acting liposomal bupivacaine compared to ropivacaine 0.2% in orthopedic trauma patients with acute pain following femur or hip fracture.

6) Inclusion and Exclusion Criteria

Inclusion criteria:

- 1) age \geq 18 years \leq 70 years
- 2) Patient's s/p trauma, with confirmed femur and/or hip fractures with a planned admission to the hospital.
- 3) Patient is ambulatory without assistance (e.g. walker, cane, caretaker) prior to incident.

Exclusion Criteria:

- 1) >10 hours since presentation to the emergency department
- 2) History of seizure disorder, recent seizure or a document intra-cranial hemorrhage.
- 3) Central or peripheral neurologic deficit on presentation
- 4) Concern or compartment syndrome
- 5) Associated additional long bone fractures
- 6) End stage liver failure
- 7) Renal failure requiring dialysis
- 8) Pregnancy or breast feeding
- 9) Prisoners
- 10) Coagulopathy with INR >1.5
- 11) Use of direct thrombin inhibitors (bivalirudin, argatroban, desirudin, dabigatran etexilate), or direct factor Xa inhibitors (rivaroxaban, apixaban, edoxaban)
- 12) Suspected prolonged intubation within first 12 hours secondary to respiratory failure other than peri-procedurally
- 13) Adults unable to consent

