- 14) Pediatric patients <18 years old
- 15) Patients exhibiting signs of shock upon admission, HR >120 or SBP <100 mmHg.
- 16) History of allergic reaction to local anesthetics
- 17) Administration of any other local anesthetic in the 2 hours prior to the study enrollment.
- 18) Distal femur fractures

7) Number of Subjects

17 patients per arm

Total subjects: 34

8) Recruitment Methods

Subjects will be recruited from the UC Davis Trauma Center. Patients found to have femur and /or hip fractures admitted to UCDMC will be screened for eligibility.

Waiver of HIPAA authorization for recruitment is requested for access to PHI during the screening to determine eligibility.

Description of PHI that will be accessed.

Information reviewed to assess eligibility will include: date of admission, date of birth, gender, mechanism of trauma injury (blunt/penetrating), x-rays, lab results, admission vital signs, home medications and the patient's medical history.

The use of PHI involves no more than minimal risk and granting of waiver will not adversely affect privacy of the patients.

Access to medical records that contain patient's personal information for the purpose of this study will be limited to the approved research personnel. These personnel already have knowledge of and access to identifiable medical information of current trauma patients as part of their daily job functions; hence, granting of this waiver will not adversely affect the privacy of the involved patients or the confidentiality of their information. EMR access to PHI is password-protected and no PHI will be reused or disclosed to any

other person or entity, except as required by law. Data will be used solely for the purposes of determining study eligibility.

The research could not practicably be conducted without a waiver or alteration.

Without an initial review of the medical record for screening purposes, it would not be possible to identify potential subjects and confirm their applicability for study participation.

The research could not practicably be conducted without access to and use of PHI.

Since PHI is embedded in the medical record and since the screening process requires detailed information about trauma patients, access to medical records (viewing of PHI) is necessary.

9) Compensation to the Subjects

Subjects will not be compensated for this study.

10) Study Timelines

The duration of each subject's participation is the length of their hospital stay.

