The patient will be blinded and all members of the healthcare team will be blinded from the point of transfer of care from the Emergency Department physicians to the receiving service.

Both groups will be able to receive as needed analgesia per the primary attending service. (e.g., oral hydrocodone/acetaminophen 5/325 mg or narcotic IV push as needed for breakthrough pain).

Patients enrolled in the study will be given a light blue wristband for identification to alert physicians regarding restrictions for anesthetics. Additionally, an automatic alert notification will be given by the Electronic

Medical Record system if additional local anesthetics are ordered for the patient.

Pain Assessment

Objective pain assessment will be evaluated by the UCDMC nursing staff per local standard of care which is every four hours while the patient is awake using a numeric rating scale (NRS) of 0 to 10 with a pain score of 0 being defined as: no pain, 1-4 mild pain, 5-7 defined as moderate pain, and 8-10 defined as severe pain.

Study Definitions

Acute and hospital-related adverse effects and study outcomes will be collected and tracked prospectively during the FICB and throughout the hospital stay, as appropriate per endpoint.

During hospital stay study outcomes

Data collection will include total amount of opioids administered to study patients in morphine equivalents (see Appendix) and the use of other analgesic medications during this time period. Adjunctive analgesic use including non-steroidal anti-inflammatory drugs, acetaminophen, and gabapentin will be quantified. Use of additional adjunctive agents such as muscle relaxants also will be collected.

All objective pain and agitation scores reported by the NRS will be collected; duration of supplemental oxygen requirement; number of episodes of oxygen desaturation (arterial O₂ sat below 92%); morning incentive spirometer and peak flow measurements; 24-hour antiemetic (e.g., promethazine; ondansetron) pharmacotherapy; time to first bowel movement; and need for anti-hallucination or anti-delirium pharmacotherapy.

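### Stable injuries elsewhere in the body stay eligible and feed the whole-patient opioid endpoint, with no baseline flag or covariate to recover the lost precision in 34 patients

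*Combined protocol and SAP*

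**What the plan says.** Section 6, inclusion 2, admits "Patient's s/p trauma, with confirmed femur and/or hip fractures with a planned admission to the hospital". It does not ask for an isolated injury. On accompanying fractures elsewhere, the only criterion is exclusion 5, "Associated additional long bone fractures".

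Several other exclusions bear on associated injury: "History of seizure disorder, recent seizure or a document intra-cranial hemorrhage", "Central or peripheral neurologic deficit on presentation", "Suspected prolonged intubation within first 12 hours secondary to respiratory failure other than peri-procedurally", and signs of shock on admission (exclusion 15). None of them removes a haemodynamically stable patient with rib, pelvic or visceral injury, or with a vertebral fracture without deficit.

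The primary endpoint in section 11 is "Total opioid requirement during the 96 hour randomization period measured in milligram morphine equivalents". It is not restricted to opioid given for the fracture. The secondary endpoint is the share of the 96 hours with a pain score above 4. Under Pain Assessment in section 12, "Objective pain assessment will be evaluated by the UCDMC nursing staff per local standard of care", with no body site named.

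Allocation is 1:1 in computer-generated blocks, with no stratification factor named (sections 12 and 30). The Statistical Analysis text compares the primary endpoint by an unpaired t-test or a Wilcoxon rank-sum test, without covariates. The outcome data listed in section 12 include neither associated injuries nor an injury severity score. The sample size is 17 per arm (section 7), given without an effect size, standard deviation or power.

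**The concern.** The block is placed below the inguinal ligament and acts on one limb, whereas the outcome sums opioid for the whole patient. In a trauma-center population some patients will probably be taking opioid for broken ribs, a pelvic fracture or an abdominal injury. Neither study drug is expected to change that part of the total. It adds spread that is unrelated to treatment and shrinks the relative difference between arms. It can also fall unevenly between two groups of 17.

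With so small a sample there is little slack. Because associated injuries are not among the listed data, the protocol does not secure what would be needed to separate this source of variation, either in this analysis or when the larger trial named in section 4 is designed.

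**Working it through.** **The plan's own figure.** The 17 per arm cannot be reproduced, because no difference, SD or power is given. Working backwards with two-sided alpha 0.05 and 80% power, the detectable difference is (1.96 + 0.84) x sqrt(2/17) = 0.96 SD by the normal approximation, or 0.99 SD by the noncentral t. At 0.5 SD, power is about 0.29-0.31.

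**Check 1: variance inflation (t-test).** Assume a share q of patients has off-target injuries that raise opioid use by m within-group SDs, equally in both arms. Total variance becomes 1 + q(1 - q)m². Start from d = 0.99, which gives 80% power when there are no such injuries.

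Example with q = 0.30, m = 1: variance 1 + 0.30 x 0.70 x 1 = 1.21, SD 1.10, d = 0.99/1.10 = 0.90, power 0.72.

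| q | m (SD) | Unadjusted power | n per arm for 80% |
|---|---|---|---|
| 0.20 | 1 | 0.74 | 20 |
| 0.30 | 1 | 0.72 | 21 |
| 0.30 | 1.5 | 0.64 | 25 |
| 0.30 | 2 | 0.54 | 31 |

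At m = 0.5, power stays at 0.78-0.79 for q from 0.10 to 0.40.

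**Check 2: simulation on an opioid-like scale.** Assumptions: 17 per arm; limb-related opioid lognormal with CV 0.6; ratio of liposomal bupivacaine to ropivacaine 0.55; other injury present with probability q, adding m times the ropivacaine-arm limb mean (itself lognormal) in both arms; 8000 runs per cell.

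The dilution can be seen directly. At q = 0.25, m = 0.5 each arm's mean rises by 0.25 x 0.5 = 0.125, so the ratio of means moves from 0.55 to 0.675/1.125 = 0.60. At m = 1 it becomes 0.80/1.25 = 0.64.

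| q | m | Wilcoxon | Log t-test | Log model with error-free flag | Gain over log t-test |
|---|---|---|---|---|---|
| 0.15 | 0.25 | 0.806 | 0.830 | 0.844 | 1.4 points |
| 0.25 | 0.5 | 0.693 | 0.731 | 0.812 | 8.1 points |
| 0.25 | 1 | 0.563 | 0.590 | 0.778 | 18.8 points |
| 0.40 | 1 | 0.437 | 0.487 | 0.724 | 23.7 points |

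Rejection under the null was 0.048-0.050. Using stratified randomisation lists as well added only about 0-2 points.

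**Sensitivity of the gain (q = 0.25).**
- Raw scale, m = 0.5: the planned t-test goes from 0.67 to 0.74 with the flag.
- 30% reduction instead of 45%, m = 0.5: log-scale power goes from 0.36 to 0.41.
- Flag with 80% sensitivity and 70% specificity: 0.744 to 0.744 at m = 0.5, and 0.590 to 0.609 at m = 1.

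**Check 3: chance imbalance.** Take two independent Binomial(17, q) counts. The probability that the arms differ by 3 or more such patients is 15% at q = 0.10, 28% at 0.20, 32% at 0.25, 35% at 0.30 and 38% at 0.40.

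**The case against.** The strongest reply is that whole-patient opioid use in injured patients is the question section 4 sets, and that randomisation protects the comparison. That stands. The effect on total opioid is a legitimate target, and unmodelled associated injuries do not bias it.

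Some stronger readings are tempting and are not supported:

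- *Polytrauma enters almost unrestricted.* The exclusions for intracranial haemorrhage, neurologic deficit, expected prolonged intubation and shock remove some of the severe cases.
- *Allocation uses a single list.* The documents say only that it is blocked and 1:1; one can say no more than that no stratification factor is named.
- *The pilot will hand the larger trial an inflated SD.* For an unadjusted trial in the same population, the spread that includes associated injuries is the right one. What is lost is the ability to split it and plan an adjusted analysis.
- *The power loss is known.* Every input to the simulations is assumed. If such injuries are rare or minor, the loss is a point or two.

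Two practical objections also stand. The gain nearly vanishes when the flag is loose, so an item such as any painful injury, without a definition, would not deliver it. And moving from Wilcoxon at 69% to a log-scale model at 81% mixes two changes, the scale and the covariate; the like-for-like gain in that cell is 8 points. Finally, the screening review in section 8 names "mechanism of trauma injury (blunt/penetrating), x-rays, lab results" but no cross-sectional imaging or injury survey, so the flag must draw on the wider trauma work-up.

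**Conclusion.** The point holds as a matter of precision. Stable injuries outside the injured limb remain eligible, their opioid counts in the primary endpoint, and nothing in the design or analysis accounts for them. A reader might infer bias, or a need for stratified randomisation; the documents and the calculations support neither.

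The size is a range conditional on assumptions. With CV 60%, a 45% reduction, 15-40% prevalence, added opioid of 0.25-1 times the limb mean and an error-free flag, the covariate is worth about 1 to 24 points of power on the log scale. It is worth less in most cases on the raw scale, with a smaller drug effect, or with a misclassified flag. An imbalance of three or more such patients arises in about 15-38% of trials at 10-40% prevalence. The change is worthwhile because it is cheap and needs no extra patients. It would not rescue a trial whose true effect is modest.

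**What to change.** 1. Before randomisation, record one yes/no item with an objective definition. For example: any fracture outside the injured hip or femur, or any thoracic, abdominal, pelvic or spinal injury documented in the trauma work-up by that time. Injuries found later should not alter the flag.
2. Prespecify that item as a covariate in the primary comparison. Use either a linear model on log total opioid, with a stated rule for zero totals, or a rank-sum test stratified by the flag. Name one of them in advance, and report the planned unadjusted test alongside.
3. Keep the randomisation as planned. Two lists would add little and would leave one stratum very small: at 25% prevalence it would hold about 0.25 x 34 = 8.5 patients.
4. Optionally, where the existing nursing assessment allows it, record a score specific to the hip or thigh to support the secondary endpoint. This may mean a second score and should not be assumed to be free.

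The cost is one case-report item, one degree of freedom and a short paragraph in the analysis plan. Eligibility, sample size and the primary endpoint are unchanged. If such injuries prove rare or minor, little is gained.
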